6.7.1 Effectiveness Analyses

Effectiveness analysis population includes all patients who are enrolled and have received at least two cycles of Obinutuzumab.

In general, the time to endpoint will be defined as an interval between the date of enrolment (date of first visit) and date of first occurrence of the event. For patients who are event free, the censoring time will be calculated as a time interval between date of enrolment and the patient's final contact with available data concerning the event. The estimates and graphical presentation will be performed via Kaplan-Meier approach.

Logistic regression will be performed on the rate of endpoints in order to test the impact of covariates, i.e. age, sex, ECOG PS, Ann Arbor staging, FLIPI, hepatitis infection (history of past/ resolved infection or latent HBV after prophylaxis as per standard treatment guidelines), chemotherapy backbone choice, medical history and history of FL, comorbidities. The list of the covariates to be included in the multivariate models will be detailed and justified in the statistical analysis plan document.

Exploratory analysis between different medical treatments given or subgroup analysis will be performed using Cox regression model and including relevant covariates. The list of the covariates to be included in the multivariate models will be detailed and justified in the statistical analysis plan document.

Further analyses will be performed to investigate different types of bias that might be present in this type of study design, e.g. time-dependent confounding, informative censoring, informative treatment changes/discontinuations, heterogeneity of results, and how to handle missing data.

Corresponding 95% confidence intervals (CIs) will be provided for all statistical estimates.

Primary endpoint

The primary endpoint is progression of disease at 2 years (POD24).

POD24 will be analyzed according to the survival analysis methods. The quartiles with their 95% confidence interval (estimated using Kaplan-Meier methods and Greenwood's formula) will be presented. Kaplan-Meier plots with a 95% CI will be prepared. Estimates for the survivor function will be obtained by the Kaplan-Meier approach.

Moreover, the POD24 will be analyzed as binary variable. Number and percentage of patients with its 95% confidence interval for POD24 will be calculated.

Logistic regression analysis will be performed to assess which variables are predictive of POD24. To identify factors associated with POD24, logistic regression analysis will be performed with backwards selection (removing factors with $P > 0.05$). Univariable associations between factors and POD24 will be calculated by using the Chi-square test.

In the analysis of POD24 will be excluded patients who die within 24 months from the treatment start with Obinutuzumab for reasons not related to the disease progression.

Secondary endpoints

Time-to-event outcomes (PFS at 2 and 3 years, TTNT, OS, TTLCB, duration of response, and time to response) will be analyzed according to the survival analysis methods. The quartiles with their 95% confidence interval (estimated using Kaplan-Meier methods and Greenwood's formula) will be presented. Kaplan-Meier plots with a 95% CI will be prepared. Estimates for the survivor functions for all time to event endpoints will be obtained by the Kaplan-Meier approach.

Cox regression analysis will be used to assess which variables are predictive of OS as well as to evaluate the association between early POD and OS from a risk-defining

event, that is, survival from time of POD for early progressors or from 2 years after diagnosis.

Response rates (ORR, CR, CR30 and rate of patients with stable disease) will be presented with the number and proportions of responders and non-responders together with two-sided, 95% Clopper-Pearson CIs.

Exploratory endpoints

All exploratory endpoints will be analyzed using descriptive statistics only.

6.7.2 Safety Analyses

Safety analysis population includes all patients who are enrolled.

Adverse events are those with start date beyond or equal to the date of first administration of Obinutuzumab and until 185 days after the last Obinutuzumab dose intake or until starting a new anti-cancer therapy (whichever occurs first). After this period AEs that are believed to be related to prior study drug treatment will be collected.

All adverse events will be assigned to a Preferred Term (PT) and will be classified by primary System Organ Class (SOC) according to the MedDRA thesaurus version 22 or higher.

Adverse events will be reported on a per-patient basis within Preferred Term. This means that even if a patient will report the same event repeatedly (i.e. events mapped to the preferred term) the event will be counted only once. In the latter case the event will be assigned the worst CTCAE severity and the strongest relationship to the study drug. The earliest date will regard as start date of the event and the latest date will regard as stop date of the event.

Data will be listed by study site, patient number, and study day. Events occurring on or after treatment on Day 1 (treatment-emergent adverse events - TEAEs) will be summarized by mapped term, appropriate thesaurus levels, and NCI CTCAE v5.0 grade. In addition, SAEs, including deaths, will be listed separately and summarized. AEs leading to treatment discontinuation will be listed.

Infusion related reactions (IRRs) and adverse events of special interest (AESI) will be summarized by descriptive statistics and will be listed.

Relevant laboratory and vital signs data will be displayed by time, with NCI CTCAE Grade 3 and 4 values identified, where appropriate. Additionally, all laboratory data will be summarized by grade with use of NCI CTCAE v5.0.

All medications reported will be coded using the WHO-DRL Dictionary version 2018 or higher and classified according to 3rd level ATC level subgroup and Preferred Term.

For clinical laboratory parameters, where appropriate, the reported values will be converted into SI units and if needed boundary values for reference ranges will be converted as well.

For each parameter the change from baseline to each post-baseline visit will be calculated. The ranges considered for such confront will be the local laboratory ranges values available at each individual site.

The following vital signs, when performed as per clinical practice, will be captured in the eCRF:

- Systolic and diastolic blood pressure (mmHg)
- Heart rate (bpm)
- Body temperature (°C)

For each variable the change from baseline to each post-baseline visit will be calculated.

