6.4.4 Safety Data Collection

Clinical AEs, serious and non-serious, will be recorded in the eCRF during the total observation period, with physician's assessment of severity (mild, moderate, severe or in oncology studies using the National Cancer Institute [NCI] Common Terminology Criteria for Adverse Events [CTCAE]) and relationship to therapy (i.e., related or unrelated) as described in Appendix 3.

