Appendix 3.3.4 Persistent or Recurrent Adverse Events

A persistent AE is one that extends continuously, without resolution, between patient evaluation time points. Such events should only be recorded once in the AE section of the CRF. The initial severity (intensity or grade) of the event will be recorded at the time the event is first reported. If a persistent AE becomes more severe, the most extreme severity should also be recorded in the AE section of the CRF. If the event becomes serious, it should be reported to the marketing authorization holder immediately (i.e., no more than 24 hours after learning that the event became serious; see Section 8.1.3.1 for reporting instructions). The AE section of the CRF should be updated by changing the event from "non-serious" to "serious," providing the date that the event became serious, and completing all data fields related to SAEs.

A recurrent AE is one that resolves between patient's evaluation timepoints and subsequently recurs. Each recurrence of an AE should be recorded separately in the AE section of the CRF.

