3.3.1 Adverse events

Adverse events are those with start date beyond or equal to the date of first administration of Obinutuzumab and until 185 days after the last Obinutuzumab dose intake or until starting a new anti-cancer therapy (whichever occurs first). After this period AEs that are believed to be related to prior study drug treatment will be collected.

All adverse events will be assigned to a Preferred Term (PT) and will be classified by primary System Organ Class (SOC) according to the MedDRA thesaurus version 22 or higher. Summary statistical tables including frequency counts and percentages and the number of adverse events will be produced.

Data will be listed by study site, patient number, and study day. Events occurring on or after treatment on Day 1 (treatment-emergent adverse events - TEAEs) will be summarized by mapped term, appropriate thesaurus levels, and NCI CTCAE v5.0 grade. In addition, SAEs, including deaths, will be listed separately and summarized.

AEs leading to treatment discontinuation will be listed.

Infusion related reactions (IRRs) and adverse events of special interest (AESI) will be summarized by descriptive statistics and will be listed.

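### The adverse event merging rule in Protocol 6.7.2 can pair one episode's grade with another's relationship and span event-free time, and it cannot supply the planned event counts

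*Protocol*

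**What the plan says.** Protocol 6.7.2 sets the unit of reporting: "Adverse events will be reported on a per-patient basis within Preferred Term". If the same term recurs in a patient, "the event will be counted only once", and "the event will be assigned the worst CTCAE severity and the strongest relationship to the study drug". On dates it adds: "The earliest date will regard as start date of the event and the latest date will regard as stop date of the event".

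Appendix 3.3.4 of the protocol governs data entry and works the other way: "Each recurrence of an AE should be recorded separately in the AE section of the CRF". The protocol synopsis and SAP 3.3.1 both plan event counts next to patient frequencies; in the SAP's words, "Summary statistical tables including frequency counts and percentages and the number of adverse events will be produced". SAP 3.3.1 neither repeats the merging rule nor replaces it.

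The treatment-emergent table in 6.7.2 is to be "summarized by mapped term, appropriate thesaurus levels, and NCI CTCAE v5.0 grade". Protocol 6.3.3 and SAP 2.4.2 list both severity and relatedness among the safety variables. Protocol 6.7.3 and SAP 3.5 plan a COVID-19 summary that covers infections.

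**The concern.** Counting a patient once per term at the worst grade is a sound way to report incidence. The rule goes further: it builds one composite event whose grade, relationship, start and stop may come from four different episodes.

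The design leaves room for this to happen:

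- Treatment is about 6 months of antibody plus chemotherapy, then about 24 months of antibody alone. Appendix 3.2 has causality judged separately for each product, so two episodes of one term can differ in their relationship to obinutuzumab.
- After 185 days from the last dose, or once a new anti-cancer therapy starts, only events believed related are collected. A recurrence picked up in that period always turns the composite event into a related one.
- Under Protocol 6.4.2 the minimal retrospective data include relationship but not grade or onset and end dates. A composite can therefore take its relationship from an ungraded early episode and its grade from a later one.

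Three things are at stake: any joint reading of severity and relatedness, the event counts, and the dating of recurrent infections for the COVID-19 summary.

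**Working it through.** No figure in either document depends on this rule, so there is no stated number to reproduce. The check is on what the rule does.

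**1. Grade and relationship.** Two episodes of one term in one patient:

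| | Grade | Related to obinutuzumab |
|---|---|---|
| Episode A | 4 | No |
| Episode B | 1 | Yes |
| Merged under 6.7.2 | 4 | Yes |

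No episode was both grade 4 and related. If episode A had itself been related, or had been the only episode, the merged record would have been right.

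**2. Size.** Inputs, all assumed because the documents give none: k episodes of the term per patient, g = P(grade 3 or higher), r = P(related), independent across and within episodes.

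- Reported as related and severe under the rule: [1 − (1 − g)^k] × [1 − (1 − r)^k]
- True probability of at least one related severe episode: 1 − (1 − g·r)^k

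With g = 0.2 and r = 0.5:

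- k = 1: 0.2 × 0.5 = 10.0% under both, so no error.
- k = 2: rule (1 − 0.8²)(1 − 0.5²) = 0.36 × 0.75 = 27.0%; truth 1 − 0.9² = 19.0%. The excess is 8.0 points, and 0.080/0.270 = 30% of the reported cases are false.

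Over g = 0.1 to 0.3 and r = 0.3 to 0.7, the false share is 19–39% for k = 2, 21–51% for k = 3 and 17–59% for k = 5.

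**3. If severity and relatedness are linked.** Keep k = 2 and r = 0.5, and let a and b be P(severe) for related and unrelated episodes.

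- Rule: 1 − [1 − ra − (1 − r)b]² − (1 − r)² + [(1 − r)(1 − b)]²
- Truth: 1 − (1 − ra)²

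| a | b | Rule | Truth | Excess (points) |
|---|---|---|---|---|
| 0.2 | 0 | 1 − 0.81 − 0.25 + 0.25 = 19.0% | 19.0% | 0 |
| 0.3 | 0.1 | 1 − 0.64 − 0.25 + 0.2025 = 31.25% | 27.75% | 3.5 |
| 0.1 | 0.3 | 1 − 0.64 − 0.25 + 0.1225 = 23.25% | 9.75% | 13.5 |

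All these percentages are among patients with two episodes of the term, not among all 300. The study-level effect scales with the share of patients who have such recurrences, which is not known.

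**4. Dates.** Two assumed 5-day episodes, 10 days affected in total. Merged span = 5 + gap + 5: 31 days for a 21-day gap, 70 for 60 days, 190 for 180 days.

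**5. Event counts.** A patient with k recorded episodes contributes 1 under the rule and k under Appendix 3.3.4. The planned number of adverse events cannot be recovered from the merged events whenever k exceeds 1.

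**6. Infections.** A merged infection term carries the start of its first episode. If that precedes the pandemic and a recurrence falls within it, the recurrence has no date of its own. SAP 3.8 expects patients enrolled both before and after the pandemic began.

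**The case against.** The strongest reply is that this is a reporting convention, not a data rule. Episodes stay separate in the CRF, data are listed by patient and study day, and the planned table is by term and grade. For patient incidence, worst-grade incidence and incidence of any related event, each tabulated alone, the rule gives the right answer. Neither 6.7.2 nor SAP Appendix 2 names a grade-by-relationship table, and AE duration is not a listed safety variable or output. All of that stands.

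It also rules out several stronger readings:

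- A reader might infer that planned tables will show severe related toxicity that did not happen. The documents do not support this, because no named table crosses the two attributes.
- A reader might illustrate the rule with a severe event in the first two cycles. Consent follows at least two induction cycles, so such an event is essentially retrospective, and its grade and dates may never be collected (Protocol 6.4.2; Appendix 2, note h).
- A reader might extend the relatedness problem to infusion-related reactions. Appendix 3.3.1 defines these as judged related to the infusion, so no unrelated severe reaction exists to be mispaired.
- A reader might put a study-level percentage on the excess. Nothing in the documents says how many patients have the discordant pattern, and the range starts at zero.
- A reader might say that the rule spoils a comparison of induction with maintenance safety. Neither document plans one.

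What the reply does not answer is that 6.7.2 expressly assigns a relationship, a start and a stop to the merged event, which an incidence table by grade does not need. Reading the rule as incidence-only is sensible, but the text does not say so and SAP 3.3.1 is silent. A programmer cannot tell whether the planned event counts should be taken before or after merging.

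**Conclusion.** The point holds in a limited form. The rule in 6.7.2 can yield a related severe event that no single episode supports, and a start-to-stop span that includes event-free time. Both need at least two episodes of the same term in one patient; the false pairing also needs discordant grade and relationship. Used as written, the rule conflicts with the number of adverse events planned in the synopsis and SAP 3.3.1, and it can misdate recurrent infections in the COVID-19 summary. The event-count conflict does not depend on any unplanned table.

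The size of the pairing error is unknown and may be zero. The illustration of 27.0% against 19.0% rests on two episodes, g = 0.2, r = 0.5 and independence. With two episodes and r = 0.5, the linked cases tried gave an excess from 0 to 13.5 points among patients with such recurrences. One-way incidence, worst-grade and any-related tables are unaffected.

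**What to change.** In Protocol 6.7.2, limit the once-per-patient, worst-grade rule to incidence tables and delete the merged start and stop dates. State the same rule in SAP 3.3.1, with these additions:

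- In any related-event table, use the worst grade among that patient's related episodes only.
- Take the number of adverse events, the timing of infections for the COVID-19 summary, and any durations from the individual episode records.

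The cost is wording and a little more programming; no new data collection is needed, because prospective recurrences are already recorded separately. The one limit is the retrospective period, where safety data are aggregate and grade or dates may be absent. Those events should be shown as grade missing or date missing, not completed from another episode.

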6.7.3 Other Analyses *The following other analyses will be performed:*

Use of Obinutuzumab in real world setting

Descriptive statistics for the use of Obinutuzumab in the real world setting will be performed.

At least the following conditions will be considered in the analysis:

- *Not performing obinutuzumab administration on Day 8 and Day 15 in Cycle 1 (without safety reasons)*
- *Maintenance period: administration of obinutuzumab in an interval superior to 10 days from the expected date (every 2 months per label). NOTE: An analysis will be performed to assess if this condition will have impact on efficacy parameters (PFS/ POD24) and to explore the delay reason (COVID-19 or others)*
- *All the chemotherapy scheme used with Obinutuzumab in real world setting*

Prescription profile

Obinutuzumab prescription profile and chemotherapy backbone choice by Italian region, age range, patient's profile and site dimension (outlying sites/universities, etc.)

Impact of COVID-19

- *Safety (infections and COVID-19 related events)*
- *Maintenance delay or interruption due to pandemic status*
- *Therapy interruption due to patient's complications caused by COVID-19*

~~The results of biomarker analyses will be presented using descriptive statistics only.~~

6.7.4 Interim and Final Analyses and Timing of Analyses

An interim analysis will be performed approximately one year after the first patient is included in the study in order to evaluate safety data, demographic data, FLIPI and treatment choices.

A second interim analysis will be performed approximately two years after the first patient included in the study in order to evaluate safety and primary and secondary effectiveness data, and the impact of COVID-19 on the patient management.

The results of the first two interim analysis will be compared.

The final Analysis will be performed at the end of the study.

6.7.5 Determination of Sample size

Sample size of this clinical study is selected based on feasibility.

Sample size is justified for the primary effectiveness endpoint POD24 treated as binary variable.

A sample size of 300 evaluable patients will allow estimation of the two-sided 95% confidence interval with a width equal to 7.9% (precision 3.95%) of the POD24 when the expected percentage is equal to 13%.

The Clopper-Pearson's formula has been used for the computation.

Table 1 provides the actual width and the precision of the 95% CI and the 95% confidence limits for different percentages of POD24 when the sample size is equal to 300 evaluable patients.

Table 1 - POD24 rate and corresponding 95% Confidence Intervals

POD24 (%)	Actual Width (%)	Precision (%)	95% Clopper-Pearson Exact CI (%)
11%	7.4	3.70	From 7.7 to 15.1
13%	7.9	3.95	From 9.4 to 17.3
15%	8.4	4.20	From 11.2 to 19.6
17%	8.8	4.40	From 12.9 to 21.7

Moreover, a sample size of 300 evaluable patients will allow estimation of the two-sided 95% confidence interval with a width equal to 9.4% (precision 4.70%) of the PFS rate at 3 years (treated as binary variable) when the expected percentage is equal to 80%.

[Table 2](#) provides the actual width and the precision of the 95% CI and the 95% confidence limits for different percentages of PFS at 3 years when the sample size is equal to 300 of evaluable patients.

Table 2 - PFS rate at 3 yrs and corresponding 95% Confidence Intervals

PFS (%)	Actual Width (%)	Precision (%)	95% Clopper-Pearson Exact CI (%)
70%	10.7	5.35	From 64.5 to 75.1
75%	10.1	5.05	From 69.7 to 79.8
80%	9.4	4.70	From 75.0 to 84.4
85%	8.4	4.20	From 80.4 to 88.8
90%	7.1	3.55	From 86.0 to 93.2

Notes: From Gallium trial, PFS at 2 years has been estimated equal to 90% while PFS rate at 3 years to 80%.

6.8 STUDY DOCUMENTATION, MONITORING, AND ADMINISTRATION

6.8.1 Study Documentation

The physician must maintain adequate and accurate records to enable the conduct of the study to be fully documented, including but not limited to the protocol, protocol amendments, Informed Consent Forms, and documentation of IRB/EC and governmental approval. In addition, at the end of the study, the physician will receive the patient data, which include an audit trail containing a complete record of all changes to the data.

The sponsor shall ensure that the dataset and statistical programs used for generating the data included in the final study report are kept in electronic format and are available for auditing and inspection.

6.8.2 Site Audits and Inspections

The physician will permit the sponsor or representative to audit facilities and records relevant to this study.

The physician will also permit national and local health authorities to inspect facilities and records relevant to this study. In case the site will receive a notice for an inspection from regulatory authority, the investigator will promptly inform the sponsor.

6.8.3 Use of Site Computerized Systems Patient's Report Outcome data will be completed by patients into a smartphone connected with a remote web-application or directly into the web-application in a computer, available at site.

When clinical observations are entered directly into a participating site's computerized medical record system (i.e., in lieu of original hardcopy records), the electronic record can serve as the source document if the system has been validated in accordance with health authority requirements pertaining to computerized systems used in clinical research. An acceptable computerized data collection system allows preservation of the original entry of data. If original data are modified, the system should maintain a

viewable audit trail that shows the original data as well as the reason for the change, name of the person making the change, and date of the change.

6.8.4 Retention of Records

Archiving at the study site has to be for 15 years after final study report or first publication of study results, whichever comes later.

Records and documents pertaining to the conduct of this study must be retained by the MAH/physician for at least 125 years after completion or discontinuation of the study, or for the length of time required by relevant national or local health authorities, whichever is longer. After that period of time, the documents may be destroyed, subject to local regulations.

No records may be disposed of without the written approval of the MAH. Written notification should be provided to the MAH prior to transferring any records to another party or moving them to another location.

All supporting functional parties will comply with the sponsor procedures regarding archiving and record management.

